1. BACKGROUND INFORMATION

1.1 Introduction

The lower urinary tract, which consists of the bladder and urethra, has a urine storage function, involving the storage of urine in the bladder, and a voiding function, involving the excretion of the stored urine. The general term for a condition where the urine storage function and urination function are impaired (storage disorder and urination disorder) is lower urinary tract dysfunction (LUTD). Symptoms caused by LUTD are called lower urinary tract symptoms (LUTS), which are classified into “storage symptoms,” “voiding symptoms,” and “post-micturition symptoms.”¹⁾ Storage symptoms include increased daytime frequency, nocturia, urinary urgency, urinary incontinence, and bladder sensation. Voiding symptoms include slow stream, intermittent stream, hesitancy, straining, and terminal dribble. Post-micturition symptoms include feeling of residual urine and post-micturition dribble. Each of these symptoms is a problem that greatly affects the patients’ activities of daily life and markedly impairs their quality of life (QOL).

[figure not shown]
In Japan, an epidemiological study on LUTS was conducted by the Japanese Continence Society in 10096 men and women aged 40 years or older (4570 included in the analysis) between November 2002 and March 2003.²⁾ The incidence of any LUTS increased with age in both men and women, and some LUTS was present in approximately 78% of the elderly aged 60 years or older. The most frequent symptoms were nocturia and increased daytime frequency, followed by slow stream, feeling of residual urine, urinary urgency, and urgency urinary incontinence in this order. When the number of patients with symptoms was estimated based on their age and sex, the number of men and women with increased daytime frequency was 15.95 million and 17.22 million, respectively, the number of men and women with slow stream was 10.88 million and 6.57 million, respectively, the number of men and women with feeling of residual urine was 7.92 million and 3.75 million, respectively, and the number of men and women with urinary urgency was 4.49 million and 4.6 million, respectively. A recent epidemiological study has reported a relationship between metabolic syndrome and LUTS, indicating that the onset of LUTS including OAB is significantly more frequent in patients with 2 or more risk factors for arteriosclerosis, which causes blood flow disturbance.³⁾ One cause of impaired urination is DU, and this is considered to manifest as underactive bladder (UAB). UAB is a condition where bladder contraction is impaired during voiding, manifesting as voiding symptoms. The most important peripheral nerve controlling the bladder is the pelvic nerve (parasympathetic nerve), and the occurrence of UAB is due to disorder of the pelvic nerve. LUTD due to bladder outlet obstruction (BOO) such as prostatic hyperplasia is impaired urination resulting from urethral obstruction, and it is reported that voiding symptoms that recur after transurethral prostatectomy are often caused not by obstruction due to recurrence of prostatic adenoma but by failure of detrusor contraction.⁴⁾ It has been reported that failure of detrusor contraction is found frequently (48%) in patients with LUTS aged 70 years or older, and that it is more common among those who have a history of urinary retention.⁵⁾ In typical UAB where the patient has little desire to void despite

a large volume of urine in the bladder, and detrusor contraction is extremely weak or absent, the patient develops dysuria, and because voiding is also inefficient, there is a large amount of residual urine. Voiding symptoms of UAB include hesitancy, slow stream, and straining. UAB is treated firstly with intermittent urinary catheterization. The main drugs used to treat UAB are cholinergics, but drug therapy is positioned as adjuvant therapy in addition to intermittent urinary catheterization and is recommended to be administered after evaluation of the therapeutic effect of intermittent urinary catheterization for 4 weeks. Drugs include bethanechol chloride and distigmine bromide. Bethanechol chloride constricts the bladder by directly stimulating muscarinic receptors, and distigmine bromide constricts the bladder by increasing the amount of free bethanechol chloride via its inhibitory effect on cholinesterase. However, since these drugs may cause a serious adverse reaction that may be fatal, attention should be paid to the onset of cholinergic crisis (acute exacerbation of the condition of excessive acetylcholine that accompanies dyspnea and requires mechanical ventilation). Among the main pathological conditions due to urine storage dysfunction is OAB. OAB involves urinary urgency as a necessary condition, and it is usually accompanied by pollakiuria and nocturia. LUTD due to BOO is urine storage dysfunction related to impaired bladder function occurring secondary to urethral obstruction, other than directly impaired urination due to urethral obstruction. In a bladder with BOO, it has been shown from animal experiments that in many cases, the volume of blood flow decreases, and in addition partial denervation occurs,⁶⁾ and partial denervation has also been observed in bladder biopsy specimens from OAB patients.^{7,8)} BOO causes the pressure inside the bladder to increase during voiding, increasing the tension in the bladder wall and leading to impaired blood flow in the bladder. As a result, the nerves inside the bladder wall (postganglionic fibers of the pelvic nerve) are susceptible to degeneration, and partial denervation develops. It is thought that this is accompanied by excessive reaction of the smooth muscle of the bladder to acetylcholine (denervation supersensitivity), leading to detrusor overactivity. OAB symptoms are storage symptoms such as urinary urgency, pollakiuria (daytime frequency and nocturia) and urgency urinary incontinence, and the filling phase is often accompanied by involuntary contraction of the bladder (detrusor overactivity).

It is known that elderly people may develop both voiding and storage symptoms. It has been reported that among elderly men with LUTS and without BOO such as prostatic hyperplasia, 40% had detrusor overactivity only, 31% had failure of detrusor contraction only, and 11% had both.⁹⁾ An epidemiological study has revealed that LUTS includes various symptoms and that both storage and voiding symptoms coexist.¹⁰⁾ Urinary urgency, nocturia, and urgency urinary incontinence are often present in patients with BOO such as prostatic hyperplasia and bladder neck sclerosis. Detrusor hyperactivity with impaired contractile function (DHIC) has been reported to be commonly present in elderly people, and inadvertent administration of anticholinergics to these patients may increase residual urine and cause urinary retention or overflow urinary incontinence.

As stated above, UAB symptoms are due to peripheral neuropathy, and since there are few therapeutics with satisfactory actions improving symptoms such as increased post void

residual, hesitancy and slow stream, efficacious therapeutics for impaired urination are to be hoped for. In addition, in some cases of OAB, impaired urine storage and impaired urination coexist and are interrelated, and it is thought to be necessary to consider the balance between both of these when administering treatment.¹¹⁾ In this case, also, no efficacious therapeutic is available.

Term	Percentage
GMOs	95
Organic	95
Natural	95
Artificial	15
GMOs	95
Organic	95
Natural	95
Artificial	15
GMOs	95
Organic	95
Natural	95
Artificial	15
GMOs	95
Organic	95
Natural	95
Artificial	15
GMOs	95
Organic	95
Natural	95
Artificial	15

Based on these findings, we have planned to conduct an early phase 2 study to evaluate the efficacy of TAC-302 in DU patients with OAB.

1.2 TAC-302 [test product]

For more information, contact the Office of the Vice President for Research and Economic Development at [contact] or [contact].

1.2.1 Mechanism of Action

Term	Percentage
GDP	100
Inflation	95
Interest rates	92
Central bank	88
Monetary policy	90
Quantitative easing	85
Inflation targeting	88
Interest rate hike	90

1.3 Placebo [Comparator]

Placebo, the comparator, contains no active ingredient of the test product and is a capsule indistinguishable from the test product in appearance.

1.4 Benefit-Risk Overview

1.4.1 TAC-302

1.4.1.1 Potential Benefits

There are few drugs to treat UAB/DU, and the development of effective drugs for impaired urination is expected.¹²⁾ In addition, in some cases of OAB, impaired urine storage and impaired urination coexist and are interrelated, and it is thought to be necessary to consider the balance between both of these when administering treatment.¹¹⁾ In this case, also, no efficacious therapeutic is available.

Since the clinical studies conducted to date enrolled healthy adults, no benefits to patients have been evaluated.

1.4.1.2 Potential Safety Risks

In conclusion, it cannot be ruled out that the findings and events observed in the non-clinical and clinical studies may also occur in this study.

1.4.2 Benefits and Risks Expected in This Study

The evaluation of PFS parameters, the IPSS, the OABSS, etc. in this study may provide the improvement of LUTS (storage, urination, and urination symptoms) in DU and OAB by treatment with TAC-302 for the study population. The pressure flow study is an invasive test to measure intravesical pressure by inserting a catheter into the bladder via the urethra and injecting water or physiological saline into the bladder to fill the bladder. Post-examination pain, hematuria, and urinary tract infection associated with catheter manipulation are most likely to occur. Usually, however, they can almost be managed by taking antibiotics and drinking water for the day to achieve diuresis.¹³⁾

1.5 Main Study Results

1.5.1 Nonclinical Studies

See the Investigator's Brochure.

1.5.2 Clinical Studies

1.5.2.1 Phase 1 Single-dose Study (Study 10054010)

1.5.2.1.1 Pharmacokinetics

1.5.2.1.2 Safety

[figure not shown]

1.5.2.2 Phase 1 Repeated-dose Study (Study 10054020)

[figure not shown]

1.5.2.2.1 Pharmacokinetics

1.5.2.2.2 Safety

[figure not shown]

1.6 Justification of Study Population and Study Design

1.6.1 Study Population

This study will target patients with OAB and voiding symptoms who have been confirmed to have DU based on the results of PFS and uroflowmetry. Patients with a strong placebo response under single-blind conditions in the observation period who do not meet the definition of OAB and voiding symptoms¹⁴⁾ at registration in the treatment period, and patients who do not meet the criteria for DU based on PFS and uroflowmetry selected with reference to past reports^{15,16)} will be deemed ineligible for registration in the treatment period, in order to select a study population which allows appropriate evaluation of the drug efficacy.

1.6.2 Study Design

1.6.3 TAC-302 Dose

1.6.4 Selection of Placebo

To objectively evaluate the efficacy and safety of TAC-302, a placebo group was established in the treatment period. PFS is currently essential for the diagnosis and evaluation of DU.²¹⁾ Although PFS is considered to have a smaller placebo effect than symptoms and QOL evaluations,¹⁷⁾ there is no evidence of variation associated with the natural course of DU or the PFS procedure in the study population of this study. Given this, as described in the objectives of the control group in the International Council for Harmonisation of Technical Requirements for Pharmaceuticals for Human Use (ICH) E10,²²⁾ it was considered necessary to establish a placebo group because it is necessary to distinguish the results occurring in

patients after the test treatment (outcomes) from the results caused by factors such as natural progression of the disease and expectations of observers/patients.

The therapeutic effect on OAB is determined by evaluation of data including the number of urinations and questionnaires, but there is a large placebo effect involved in the evaluation of these. Accordingly, for studies verifying the clinical effect of OAB therapeutics, a placebo-controlled double-blind study is recommended.^{17,18,19)} Evaluation of OAB symptoms in this study is a secondary endpoint, but it was considered to be necessary to establish a placebo group to evaluate OAB symptoms.

2. STUDY OBJECTIVES

2.1 Primary Objective

To investigate the efficacy of TAC-302 in DU patients with OAB, using evaluation of the BCI (males) or PIP 1 (females) at each time point as an indicator.

2.2 Secondary Objectives

- (1) To investigate the efficacy of TAC-302 in DU patients with OAB, using the changes in values including PFS parameters, uroflowmetry parameters, BVE, the IPSS or the OABSS as indicators.
- (2) To investigate the efficacy of TAC-302 in DU patients with OAB in comparison with placebo.
- (3) To investigate the safety of TAC-302 in DU patients with OAB using data including the incidence of adverse events and adverse reactions as indicators.

2.3 Endpoints

2.3.1 Primary Endpoint

- BCI [maximum detrusor pressure at peak urine flow ($P_{det}Q_{max}$) + 5 × peak urine flow rate (Q_{max})] (males)
- PIP1 ($P_{det}Q_{max} + Q_{max}$) (females)

[Evaluation time points: week 0, week 12]

2.3.2 Secondary Endpoints

2.3.2.1 Efficacy

- (1) PFS parameters (filling phase) [Evaluation time points: week 0, week 12]
 - Volume at first desire to void
 - Maximum bladder volume
 - Bladder compliance
 - Appearance of bladder involuntary contraction
 - Bladder volume up to appearance of bladder involuntary contraction
- (2) PFS parameters (voiding phase) [Evaluation time points: week 0, week 12]
 - Detrusor pressure at start of voiding ($P_{det\ open}$)
 - Maximum detrusor pressure ($P_{det\ max}$)
 - Maximum flow rate (Q_{max})

- Average flow rate (Q_{ave})
- Detrusor pressure at maximum flow ($P_{det}Q_{max}$)
- Duration of bladder contraction
- Voided volume
- Post void residual

(3) Uroflowmetry parameters [Evaluation time points: weeks 0, 4, 8, 12]

- Maximum flow rate (free Q_{max})
- Average flow rate (free Q_{ave})
- Voided volume
- Voiding time

(4) Post void residual measured by ultrasonography [Evaluation time points: at registration in observation period, weeks 0, 4, 8, 12]

(5) BVE [Voided volume / (voided volume + post void residual)] [Evaluation time points: weeks 0, 4, 8, 12]

Calculated from the voided volume measured by uroflowmetry and the post void residual measured by ultrasonography

(6) Change in IPSS score at weeks 4, 8, and 12 of the treatment periods relative to baseline (week 0)

- IPSS total score
- IPSS storage symptoms score
- IPSS voiding symptoms score
- IPSS QOL score

(7) Change in IPSS score at weeks 4, 8, and 12 of the treatment periods relative to baseline (week 0)

(8) Change in KHQ score (by domain) at week 12 of the treatment period relative to baseline (week 0)

(9) Change in bladder diary record data at weeks 4, 8, and 12 of the treatment periods relative to baseline (week 0)

- Average number of micturition per 24 hours
- Average number of urgency urinary incontinence episodes per 24 hours
- Average number of urinary urgency episodes per 24 hours
- Average voided volume per urination
- Average number of nocturnal urinations

2.3.2.2 Safety

(1) Occurrence of adverse events and adverse reactions

(2) Blood pressure, pulse rate, body temperature, 12-lead electrocardiogram, and laboratory tests

3. STUDY DESIGN

This study is a central-registration, multi-center, double-blind, placebo-controlled, randomized parallel-group comparative study to investigate the efficacy and safety of TAC-302 in DU patients with OAB. The design of this study is shown in [Figure 3-1](#). This study is composed of a single-blind observation period, a double-blind treatment period, and a follow-up period.

Patients considered eligible for the enrollment in the observation period after providing written informed consent will proceed to the observation period. The investigational drug for the observation period will be administered under single-blind conditions. In the observation period, the investigational drug (placebo) will be administered orally twice daily after breakfast and dinner for 2 to 4 weeks. Patients considered eligible for the enrollment in the treatment period after the end of the observation period will proceed to the treatment period. The investigational drug for the treatment period will be administered under double-blind conditions. The investigational drug in the treatment period will be randomly assigned, with patients allocated to the TAC-302 and placebo group in a 2:1 ratio. To maintain a balance between groups, dynamic assignment using assignment factors [sex (male and female), age at informed consent (< 65 years and \geq 65 years)] will be performed. In the treatment period, the investigational drug (TAC-302 200 mg or placebo) will be administered orally twice daily after breakfast and dinner for 12 weeks. After the start of the treatment period (registration in the treatment period), patients will make visits in weeks 2, 4, 8, and 12, and the designated observations and tests will be performed. A follow-up examination will be performed 1 week after the end of week 12 of the treatment period. If any adverse event is considered to be an adverse reaction after the follow-up examination, the follow-up investigation should be performed until it is confirmed that the symptom (including abnormal laboratory values) has recovered to the state of before the onset as much as possible or is resolving.

[figure not shown]

Figure 3-1 Study Design

3.1 Study Period

Study initiation date (planned): August 2017

Study completion date (planned): December 2019

[Region/Country]: Japan

3.1.1 Definition of Each Period for Each Patient

Each period described in this protocol is defined as follows.

Study period:	From the time of obtaining informed consent to the end of the follow-up examination
Observation period:	The period from registration in the observation period up to registration in the treatment period (registration in the treatment period will be performed between 2 to 4 weeks after registration in the observation period)
Treatment period:	From the time of registration in the treatment period to the end of week 12 of the treatment period
Follow-up period:	From the end of week 12 of the treatment period to the end of the follow-up examination (performed 1 week after the end of week 12 of the treatment period)

3.2 Patient Assignment and Blinding

3.2.1 Method of Assignment

This study is a randomized study conducted by central registration using an Interactive Web Response System (IWRS). Data will be entered according to the IWRS procedure.

The principal investigator or subinvestigator will provide each target patient with an explanation and then obtain written informed consent. A patient identification code will consist of a TAC302-site number (2 digits) - the order of consent obtainment at each site (3 digits). After it is confirmed that the patient meets the inclusion criteria and does not meet any exclusion criteria for registration in the observation period and has no problems with his/her eligibility, the patient will be enrolled in the observation period via the IWRS. After it is confirmed that the patient meets the inclusion criteria and does not meet any exclusion criteria for registration in the treatment period and has no problems with his/her eligibility, the patient will be enrolled in the treatment period via the IWRS.

When the registration in the treatment period is complete, patients will be randomly assigned to the TAC-302 group and the placebo group in a ratio of 2:1 via the IWRS based on a dynamic allocation method (minimization method) including the stochastic process.

Patients will be stratified according to the following assignment adjustment factors:

- Sex (male or female)
- Age at informed consent (< 65 years or \geq 65 years)

The IWRS will assign an investigational drug to each patient, notify the study site of the drug number assigned to the patient, and give instructions for prescription of the investigational drug. Detailed information will be provided in the IWRS procedure.

If an investigational drug different from the drug number assigned by the IWRS should be dispensed in error to a patient, the site must notify the sponsor immediately. The site must also document the cause of investigational drug prescribing or dispensing errors. If a patient starts to receive an investigational drug in a group different from the group to which he/she has actually been assigned, administration of the investigational drug will be continued.

3.2.2 Blinding

This study is a double-blind study. During the conduct of the study, neither any of the patients, nor the principal investigator, subinvestigator, study coordinator, or sponsor will be informed about the treatment groups. Key codes will be prepared and unblinded according to the procedures for investigational drug assignment. The investigational drug assignment manager will store and manage the key codes until unblinding.

The following details will be shown in documents such as the procedures for investigational drug assignment, the emergency key code unblinding procedure or the key unblinding procedure.

- The method for assuring indistinguishability (the timing, person performing the procedures, the items carried out, etc.)
- Methods for storing, managing and handling key codes and emergency key codes and identification of the person storing the key codes
- Emergency key code unblinding procedure
- Timing and procedure for unblinding after data lock

4. SELECTION AND WITHDRAWAL OF PATIENTS

4.1 Inclusion Criteria

At each registration, patients meeting all of the following inclusion criteria will be eligible.

The rationale is shown in Section [14.3](#).

4.1.1 Registration in the Observation Period

- (1) Provided written informed consent in person
- (2) Aged ≥ 20 years at the time of obtaining informed consent and able to receive treatment as an outpatient (irrespective of sex)
- (3) Being able to use the toilet himself/herself and make accurate bladder diary records, in the opinion of the principal investigator or subinvestigator
- (4) Having had lower urinary tract symptoms (storage symptoms, voiding symptoms, and post-micturition symptoms) for at least 12 weeks before registration in the observation period
- (5) Scoring ≥ 2 points on any of the following questions for the IPSS voiding symptoms score at registration in the observation period
 - Over the past month, how often have you found you stopped and started again several times when you urinated?
 - Over the past month, how often have you had a weak urinary stream?
 - Over the past month, how often have you had a push or strain to begin urination?
- (6) Scoring ≥ 2 points for the urinary urgency score (Question 3), and having an OABSS total score of ≥ 3 points in OABSS evaluation at registration in the observation period
 - Question 3: How often do you have a sudden desire to urinate, which is difficult to defer?
- (7) Post void residual ≤ 300 mL measured at registration in the observation period

4.1.2 Registration in the Treatment Period

- (1) Scoring ≥ 2 points on any of the following questions for the IPSS voiding symptoms score at registration in the observation period
 - Over the past month, how often have you found you stopped and started again several times when you urinated?
 - Over the past month, how often have you had a weak urinary stream?
 - Over the past month, how often have you had a push or strain to begin urination?
- (2) Meeting all of the following conditions based on information from bladder diary records in the 3 days directly before registration in the treatment period
 - 1) Being able to use the toilet himself/herself and make accurate bladder diary records, in the opinion of the principal investigator or subinvestigator
 - 2) An average of ≥ 8 urinations per 24 hours and meeting either of the following conditions
 - An average of ≥ 1 urinary urgency episodes per 24 hours
 - An average of ≥ 1 urgency urinary incontinence episode per 24 hours

- (3) Post void residual ≤ 300 mL measured at registration in the treatment period
- (4) Meeting the following criteria based on a urodynamic study (UDS) performed at registration in the treatment period
 - [a, b: Calculated from PFS parameters, c: Calculated from uroflowmetry parameters and the measurement of the post void residual according to ultrasound]

- 1) Criteria for males
 - a) $BCI (P_{det}Q_{max} + 5Q_{max}) < 100$
 - b) Bladder outlet obstruction index ($BOOI = P_{det}Q_{max} - 2Q_{max} < 40$)
 - c) BVE [voided volume / (voided volume + post void residual)] < 90%
- 2) Criteria for females
 - a) $P_{det}Q_{max} < 20$
 - b) $Q_{max} < 15$
 - c) BVE [voided volume / (voided volume + post void residual)] < 90%

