4.2.2 Registration in the Treatment Period

- (1) A rate of compliance with administration of the investigational drug of <80% in the observation period
- (2) Having the following concurrent conditions, and having been diagnosed with neurogenic bladder accompanied by obvious neurological abnormality associated with the following diseases
 - 1) Cerebrovascular disorder (cerebral hemorrhage, cerebral infarction, etc.)
 - 2) Parkinson's disease
 - 3) Alzheimer's disease
 - 4) Multiple sclerosis
 - 5) Spina bifida
 - 6) Spinal cord disorder (spinal cord injury, etc.)
- (3) Concurrent urinary disease impairing determination of the effect of the investigational drug, such as urinary tract infection (prostatitis, cystitis, etc.), cystitis interstitial, urinary tract stenosis, urinary tract obstruction, calculus urinary (calculus ureteric, calculus urethral, calculus bladder, etc.), benign tumor of the urethra (urethral polyp, cyst, papilloma, etc.) and urethral diverticulum.
- (4) Concurrent bladder cancer or prostate cancer, or suspected bladder cancer or prostate cancer
- (5) Cystocele classified as stage III or higher according to the POP-Q stage classification (females)
- (6) Overflow urinary incontinence
- (7) Clinically significant concurrent conditions (including symptoms and findings) such as severe liver disease (hepatitis viral, drug-induced liver injury, etc.), severe renal disease (acute renal failure, glomerulonephritis, nephritis interstitial, etc.), severe cardiovascular disease (cardiac failure congestive, symptomatic unstable angina pectoris, poorly controlled arrhythmia, myocardial infarction, etc.), severe blood dyscrasia (pancytopenia, leukopenia, etc.), severe respiratory disease (bronchial asthma, bronchitis chronic, etc.), severe digestive disease (peptic ulcer, reflux esophagitis, Crohn's disease, colitis ulcerative, etc.), severe neuropsychiatric disease (schizophrenia, dementia, etc.), severe immune disease (collagen disorder, etc.), severe metabolic or endocrine disease or malignant tumor

- (8) Having received urethral catheter placement, or performing intermittent self-catheterization due to the inability to urinate spontaneously
- (9) Being determined to be ineligible for this study in the opinion of the principal investigator or subinvestigator

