Checking of drug compliance			X	X		X		X		X		X
Physical examination	X		X	X		X		X		X	X	X
Blood pressure, pulse rate, and body temperature	X ⁹⁾		X	X		X		X		X	X	X
12-lead electrocardiography	X ⁹⁾		X							X	X	X
Laboratory tests ³⁾	X ⁹⁾		X	X		X		X		X	X	X
Pregnancy tests ⁴⁾	X											
Bladder diary records: Supplied	X			X		X		X				
Filled in												
Collected			X			X		X		X		X
Checked			X			X		X		X		X
Symptom score (IPSS, OABSS) evaluation	X		X			X		X		X		X
King's health questionnaire evaluation			X							X		X
Pressure Flow Study (PFS) ¹⁰⁾			X							X		X
Uroflowmetry			X ¹¹⁾			X ¹¹⁾		X ¹¹⁾		X ¹¹⁾		X ¹¹⁾
Post void residual measured by ultrasound	X ⁹⁾		X ¹¹⁾			X ¹¹⁾		X ¹¹⁾		X ¹¹⁾		X ¹¹⁾
Prostate gland volume measurement	X ⁹⁾											
Checking concomitant drugs/concomitant therapy ¹²⁾												X
Checking adverse events ¹²⁾												X

- 1) Obtaining informed consent: Obtained within the period of 28 days before registration in the observation period.
- 2) Assigning of patient identification codes: Assigned to patients providing informed consent.
- 3) Laboratory tests: Hematology tests, biochemistry tests, endocrinological tests and urinalysis will be performed. However, the urinalysis test urine sediment will only be performed at registration in the observation period and at registration in the treatment period.
- 4) Pregnancy tests: Required for female patients with childbearing potential. However, a pregnancy test will not be required for patients more than 1 year after menopause or patients in whom the possibility of pregnancy is medically ruled out. At tests before registration in the observation period, pregnancy tests (serum or urine) must be negative. The time window for performing the test is the period of 7 days before registration in the observation period.
- 5) Time window for registration in the treatment period: All observation and examination items at registration in the treatment period will be performed by registration in the treatment period, 2 to 4 weeks after registration in the observation period.
- 6) Time window for visits in the treatment period: Visits at weeks 2, 4, and 8 of the treatment periods will be allowed to be within the range of the standard date ± 3 days. The visit at week 12 will be allowed to be within the range of the standard date -3 days to the standard date $+7$ days.

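### The voiding-symptom criterion for entering the treatment period is scored before the placebo run-in, so it cannot screen out placebo responders as Protocol 1.6.1 requires

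*Protocol*

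**What the plan says.** Protocol 4.1.2 lists the inclusion criteria for the treatment period. Item (1) asks for at least 2 "points on any of the following questions for the IPSS voiding symptoms score at registration in the observation period". The three questions cover intermittency, weak stream and straining. Protocol 4.1.1(5), for entry to the observation period, has the same text, and the synopsis repeats it in its own list for the treatment period.

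Protocol 1.6.1 describes a screen after the run-in. It names "Patients with a strong placebo response under single-blind conditions in the observation period who do not meet the definition of OAB and voiding symptoms", judged at the second registration, and says that they "will be deemed ineligible for registration in the treatment period". It names patients who fail the detrusor underactivity criteria as a separate group.

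On which text governs entry, Protocol 4.1 says "At each registration, patients meeting all of the following inclusion criteria will be eligible", and 3.2.1 makes enrolment through the IWRS conditional on those lists: "After it is confirmed that the patient meets the inclusion criteria and does not meet any exclusion criteria for registration in the treatment period".

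**The concern.** A score taken before the first placebo capsule cannot show a response to placebo. If sites follow 4.1.2(1) as printed, the OAB part and the urodynamic part of the 1.6.1 screen operate, but the voiding-symptom part does not.

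Two things are at stake. The first is the population: 1.6.1 intends patients to have voiding symptoms when treatment starts, and the listed criteria do not secure that. The second is the IPSS voiding endpoints. SAP 8.1.6 analyses the voiding score and questions 1, 3, 5 and 6 as change and percentage change from Week 0, and patients with few voiding symptoms at Week 0 have little room to improve on them. A Week 0 voiding score of 0 also leaves the percentage change undefined.

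These patients would also stay in the per protocol set, the primary efficacy set under SAP 3.2. Its first exclusion covers violations of the inclusion criteria, and a low Week 0 score does not violate 4.1.2(1) as written. If some sites used the Week 0 score and others the printed rule, entry also differed between sites.

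**Working it through.** The plan gives no figure to reproduce. The check compares texts, with a short calculation of score ranges.

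**1. Is the criterion a duplicate?**

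| Rule | Questions | Threshold | Score used |
|---|---|---|---|
| 4.1.1(5) | IPSS 3, 5, 6 | 2 or more on any | first registration |
| 4.1.2(1) | IPSS 3, 5, 6 | 2 or more on any | first registration |
| Synopsis, treatment-period item (1) | IPSS 3, 5, 6 | 2 or more on any | first registration |

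Every patient at the second registration has already passed 4.1.1(5). The same condition applied to the same score can exclude nobody who was validly enrolled.

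**2. Does another rule do the job?**

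| Feature | Rule | Data used | After the run-in has begun? |
|---|---|---|---|
| OAB | 4.1.2(2) | diary, 3 days before second registration | yes |
| Post void residual | 4.1.2(3) | second registration | yes |
| Detrusor underactivity | 4.1.2(4) | "urodynamic study (UDS) performed at registration in the treatment period" | yes |
| Voiding symptoms | 4.1.2(1) | first registration | no |

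Item (4) measures urodynamic function, which 1.6.1 treats as a separate condition, so it does not replace a symptom test. In 4.2.2, no exclusion tests voiding symptoms. The only remaining route is item (9), "Being determined to be ineligible for this study in the opinion of the principal investigator or subinvestigator", which sets no common standard across sites.

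**3. Is a Week 0 score available in time?** Yes. In Table 5-2 the row "Symptom score (IPSS, OABSS) evaluation" is marked at both registrations, and footnote 5 requires the Week 0 items to be done by the second registration. No eligibility rule uses that score.

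**4. What can such a patient score?** Section 1.6.1 gives no cut-off, so I assume the threshold of 4.1.1(5). The IPSS total runs to 35 over 7 questions, so each item runs from 0 to 35/7 = 5. The voiding score is Q1 + Q3 + Q5 + Q6 (Protocol 11.3.1, SAP 6.1.1.3.1), with maximum 4 × 5 = 20.

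- Below 2 on all three questions: Q3 + Q5 + Q6 is 0 to 3 × 1 = 3, out of 3 × 5 = 15. The voiding score is 0 to 3 + 5 = 8.
- At least 2 on one question: the voiding score is 2 to 20.

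Hence 0 or 1 occurs only below the cut-off, 2 to 8 occurs in both groups, and 9 to 20 occurs only in patients who pass. SAP 8.1.6 already summarises the Week 0 voiding score, and SAP 6.2.2.1 includes the minimum. A minimum of 0 or 1 would prove that such a patient was randomised. A higher minimum would not rule it out, so a count needs a patient listing.

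**5. How well would a Week 0 score detect placebo response?** The IPSS asks about the past month and the run-in lasts 2 to 4 weeks. Taking a month as 28 to 30.4 days, the share of the recall window before placebo is:

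- 2-week run-in: (28 − 14)/28 = 50% to (30.4 − 14)/30.4 = 54%.
- 4-week run-in: (28 − 28)/28 = 0% to (30.4 − 28)/30.4 = 8%.

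For the score taken at the first registration, the whole window predates placebo.

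**The case against.** The strongest reply is that this is a copying slip. Items (2) to (4) of 4.1.2 all use the second registration. The protocol has similar slips: secondary endpoint (7) in 2.3.2.1 repeats the IPSS although OABSS is a stated endpoint, and 5.1.15 on uroflowmetry refers to the pressure flow study. Sites and the IWRS may have used the Week 0 score, and the IWRS procedure is not available to check. The rationale in 14.3.1.2 is not visible either. This is fair, and it means that what was done is unknown. It does not change the rule as printed, which appears in two places and which 3.2.1 makes a condition of enrolment.

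Second, the effect is limited. Each randomised patient must still meet objective limits at Week 0: BVE below 90% for all, BCI below 100 and BOOI below 40 for men, detrusor pressure at maximum flow below 20 and maximum flow below 15 for women. The IPSS MMRM adjusts for baseline, and SAP 8.1.12 analyses outcomes by baseline IPSS total and QOL score. The voiding score of an affected patient could still fall by up to 8 points, because question 1 is not part of the criterion. All of this stands and limits the point to the population and the IPSS voiding endpoints. None of it restores the missing screen.

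Third, Week 0 is the IPSS baseline, so a threshold there selects on the baseline value and adds regression to the mean to the within-group paired tests and change summaries. That is a real cost. It affects both arms alike and leaves the randomised comparison intact.

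**Conclusion.** The concern holds. Followed as written, 4.1.2(1) admits patients whom 1.6.1 declares ineligible and keeps them in the primary efficacy set. This should be corrected, but it does not threaten the main result: the limits on bladder function are tested at Week 0 and the comparison between arms stays valid.

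The textual mismatch is certain. The number of patients affected cannot be derived from the documents. The score ranges rest on the assumed 2-point cut-off, and the intent is read from 1.6.1 alone.

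**What to change.** Reconcile 4.1.2(1) and its synopsis copy with 1.6.1 on the scoring time. Agreement with 1.6.1 means using the IPSS already scheduled at Week 0, with the 2-point threshold stated explicitly as the cut-off if that is what is meant.

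Enrolment is probably complete: the planned completion date was December 2019, and SAP version 2.0 is dated 08 January 2020 and records changes made before unblinding. In that case, before unblinding:

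- list the patients scoring below 2 on all three questions at Week 0;
- confirm which time point the sites applied;
- record how the per protocol set treats these patients, by the sponsor and medical-expert route in Protocol 13.1.2.1. Keeping them follows the definition as written; excluding them departs from it and needs a stated reason.

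The cost is one phrase in two places, or one blinded listing, a site confirmation and a recorded decision. No assessment is added. A Week 0 test would mean somewhat more run-in failures, the regression to the mean described above, and only a partial screen after a short run-in. Excluding patients afterwards would make the per protocol set smaller.
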